9.1.2. Rationale for study design

NOAD represent a heterogeneous group of diseases with different clinical conditions and disease progression. Some NOAD present with a chronic disease pattern of relapse over time e.g. multiple sclerosis or systemic lupus erythematous, or an acute disease pattern (e.g. Guillain Barré Syndrome).

In addition to the comparison of the exposed vs. non-exposed cohort (cohort design), the confirmed NOAD in the exposed cohort will also be analysed using a self-control case-series (SCCS) analysis.

In the cohort design, specified NOAD will be collected over a period of one year following the administration of at least one dose of Cervarix in an exposed cohort and over a comparable period in the unexposed cohorts as shown in Figure 1. Four cohorts will be constituted as shown in Figure 1. The unexposed male cohorts will be enrolled in order to assess a possible change over time in the incidence rate of NOAD in CPRD GOLD independent of Cervarix introduction. The cohorts will be frequency

116239 (EPI-HPV-040 VS UK)

Protocol FDA - EMA PASS Final Version 1 matched for the age (age class of one year) and practice region identifier at reference date (age at first dose of Cervarix).

An unexposed concurrent female cohort has been not chosen as the unvaccinated group for the following reasons:

- There is a under-reporting of HPV vaccination in CPRD GOLD as evidenced by the difference in vaccine coverage in CPRD GOLD population and the UK population (see Table 2), an exposed concurrent cohort would include both true and false unexposed subjects;
- Moreover, because of the large vaccine coverage in the UK, non-vaccinated women could have different health care behaviour compared to the vaccinated women, resulting in a difference in the probability to detect auto-immune disease.

Therefore, the reference date (time = 0) for the vaccinated (exposed) cohort will be the date of the first dose of Cervarix recorded in CPRD GOLD. The reference date for the unexposed (unvaccinated) cohorts will be a date randomly selected among the reference dates of the exposed subjects and minus 3 years for the historical cohorts.

[figure not shown]
Figure 1 Cohort design

Note: all three doses may not have been administered

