9.2.1. The UK HPV National Immunization Programme

The submitted study is in the UK, which is a country with a high Cervarix vaccine coverage. The recommended schedule in the UK for routine HPV vaccination of all girls at 12 to 13 years of age is [DH, 2008; HPA, 2010]:

- Vaccination at this age starts with a first dose of 0.5ml of Cervarix HPV vaccine
- The second dose of 0.5ml follows one to two months after the first dose
- A third dose of 0.5ml follows at least six months after the first dose

The UK has had sufficient Cervarix vaccination coverage to, in theory, enable data acquisition. A public immunisation programme targeting girls between 12-13 years of age including a catch-up programme for young women up to 18 years was undertaken during the academic year 2008/09. A phased catch-up programme for females born 1 September 1991 to 31 August 1995 during the 2008/09 academic year was completed by the end of the 2009/10 academic year. The programme was delivered largely through secondary schools [Crawford, 2009; Sheridan, 2009; Sheridan, 2010]. In the UK public HPV immunization program (12-13 year olds), HPV vaccination coverage in the UK for 2010/11 was 89.0%, 87.6% and 83.8% for the first, second and third dose respectively [Health Protection Agency, 2012]. The recommended age range for the UK programme matches the age range required by the FDA (9-25 years of age) for the post-licensure safety study.

The study population will be composed of female and male subjects, 9 to 25 years of age, registered in the CPRD GOLD.

The exposed cohort will be composed of female subjects vaccinated with at least one dose of Cervarix, with or without other recommended vaccines.

The unexposed historical female cohort will consist of frequency age-matched and practice region-matched female subjects from the period before the introduction of Cervarix. The unexposed concurrent male cohort will consist of frequency age-matched and practice region-matched by one-year classes (15, 16, 17, etc.) male subjects from the

period after the introduction of Cervarix. The unexposed historical male cohort will consist of frequency age-matched and practice region-matched male subjects from the period before the introduction of Cervarix.

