9.2.2. Cohort identification and creation

The exposed eligible cohort have been identified based on the stepwise approach defined in Annex 5. Among eligible exposed subjects, 65,000 subjects will be randomly selected using the RANUNI function of SAS. The RANUNI function returns a number that is generated from the uniform distribution on the interval (0, 1). The corresponding subject number will be computed as *random_subj_number=ranuni(seed)*. The subjects will be ordered according the *random_subj_number* and the first 65,000 subjects will be included in the exposed cohort.

The unexposed eligible cohorts have been identified based on the stepwise approach define in Annex 5.

All the unexposed subjects who matched exposed subject for age (birth cohort) and region (frequency matching) will be identified. This represents 234 combinations of birth cohort-region (18 birth cohorts and 13 regions in CPRD GOLD). In each combination, the subjects will be randomly selected based on the distribution in the exposed cohort.

A reference date is randomly attributed to all potential unexposed subjects. For the concurrent male cohort, the reference date is a random date between 01-SEP-2008 and 31-AUG-2010. For the historical cohorts, the reference date is a random date between 01-SEP-2005 and 31-AUG-2007 (reference dates for exposed cohort – 3 years).

The random reference dates in each 'birth cohort-region" combination will be attributed randomly using the RANUNI function of SAS.

The age at reference date will be calculated for the unexposed cohort. After applying the exclusion criteria, the eligible subjects (65,000 subjects in each cohort) will be randomly selected in each of the combinations 'birth cohort-region' taking into account the distribution in the exposed cohort. The random selection will also use the RANUNI function of SAS.

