9.3.2. Secondary endpoints

Secondary endpoint is the occurrence of new onset of individual confirmed autoimmune disease during the following specific periods:

- Occurrence of Guillain Barré syndrome (including Miller Fisher syndrome and other variants), and autoimmune haemolytic anaemia within two months following the administration of the first dose of Cervarix;
- Occurrence of idiopathic thrombocytopenic purpura (ITP) within six months following the administration of the first dose of Cervarix;
- Occurrence of multiple sclerosis, transverse myelitis, optic neuritis, other demyelinating diseases (see the two sub-bullets for these diseases in Section 9.3.1), auto-immune uveitis, systemic lupus erythematous (SLE), rheumatoid arthritis (RA), juvenile rheumatoid arthritis (JRA), Still's disease, psoriatic arthritis, ankylosing spondylitis, type 1 diabetes mellitus, auto-immune thyroiditis (including Hashimoto's disease, Graves'/Basedows' disease), and inflammatory bowel / hepatic disease (Crohn's disease, ulcerative colitis and autoimmune hepatitis) within one year following the administration of the first dose of Cervarix.

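### Sections 9.1.2 and 9.2.2 give conflicting rules for time zero in the unexposed cohorts; the 9.2.2 rule can misalign season in the 2- and 6-month windows and age within birth cohorts.

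*Protocol*

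**What the plan says.** Section 9.1.2 sets time zero for an exposed girl at her first recorded Cervarix dose. For the comparison cohorts it states: "The reference date for the unexposed (unvaccinated) cohorts will be a date randomly selected among the reference dates of the exposed subjects", with 3 years subtracted for the historical cohorts.

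Section 9.2.2, which describes how the cohorts are built, uses other words. For males: "For the concurrent male cohort, the reference date is a random date between 01-SEP-2008 and 31-AUG-2010". For the two historical cohorts: "For the historical cohorts, the reference date is a random date between 01-SEP-2005 and 31-AUG-2007". A parenthesis after these limits mentions the exposed cohort's reference dates less 3 years. The dates in each birth cohort-region "combination will be attributed randomly using the RANUNI function of SAS", a generator that the same section describes as uniform on (0, 1). Age at the reference date is calculated after the date has been assigned.

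Section 9.2.1 says of the vaccination campaign: "The programme was delivered largely through secondary schools". It also describes a phased catch-up organised by academic year. No monthly distribution of first doses is given.

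Section 9.3.2 sets a window of two months for Guillain-Barré syndrome (GBS) and autoimmune haemolytic anaemia, six months for ITP, and one year for every other disease. Section 9.7.6 reports a rate per cohort for each disease, fits a Poisson ratio only above 10 cases, and calls these analyses non-confirmatory.

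**The concern.** A retrospective cohort needs one definition of time zero. A programmer working from 9.1.2 would reproduce the calendar pattern of real first doses. One working from 9.2.2 would spread the dates over 24 months, summer holidays included.

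If first doses cluster, two things follow from the 9.2.2 rule:

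- **Season.** Exposed windows start in campaign months, while unexposed windows start throughout the year. A 12-month window covers every season wherever it starts. A 2- or 6-month window does not.
- **Age.** A birth cohort vaccinated mainly in one academic year is compared with subjects whose dates run over two, so mean age at the reference date can differ within that birth cohort.

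The male comparison would not reveal a seasonal mismatch, because both male cohorts get their dates by the same 9.2.2 rule. Season is also not among the covariates in 9.7.9.1.

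**Working it through.** **1. The plan's own dates.** 01-SEP-2008 to 31-AUG-2010 less 3 years is 01-SEP-2005 to 31-AUG-2007, 730 days in each case. The stated limits reproduce, so the conflict concerns how dates are drawn within them.

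**2. The two rules side by side.**

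| | 9.1.2 | 9.2.2 |
|---|---|---|
| Concurrent males | an exposed subject's first-dose date | random date between two limits |
| Historical cohorts | an exposed subject's date less 3 years | random date between two limits; a parenthesis mentions the exposed dates less 3 years |

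The rules agree only if first doses are evenly spread over the span.

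**3. Seasonal sensitivity (assumed inputs).** Let incidence over the year be 1 + A·cos(2π(t − p)/12), with t in months, amplitude A and peak month p. Let window length be w months and let first doses be spread evenly over a season of s months. With no vaccine effect, and with unexposed dates uniform over the year, the exposed/unexposed ratio lies within

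1 ± A · g(w) · g(s), where g(m) = sin(πm/12) / (πm/12),

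the ends being reached at the least favourable peak month. The values needed are g(2) = 0.955, g(6) = 0.637, g(12) = 0, g(3) = 0.900 and g(10.5) = 0.139.

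| First doses (assumed) | A | 2 months | 6 months | 12 months |
|---|---|---|---|---|
| September-November, s = 3 | 0.30 | ±0.30 × 0.955 × 0.900 = ±0.258 | ±0.30 × 0.637 × 0.900 = ±0.172 | 0 |
| September-November, s = 3 | 0.20 | ±0.172 | ±0.115 | 0 |
| September to mid-July, s = 10.5 | 0.30 | ±0.30 × 0.955 × 0.139 = ±0.040 | ±0.30 × 0.637 × 0.139 = ±0.027 | 0 |

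If unexposed dates are drawn from the first-dose dates, the start-month distributions match by design and the seasonal ratio is 1.00 for all windows.

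**4. Age (assumed inputs).** Suppose a birth cohort is vaccinated evenly within the first academic year. Its mean start is month 6 of the 24-month span, against month 12 for uniform dates, so comparators are 6 months older on average. For a birth cohort vaccinated in the second year the shift is 12 − 18 = −6 months. The signs are opposite, so pooled shifts may partly cancel.

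**5. Cases at stake.** Expected cases per cohort = 65,000 × rate × w/12, with full follow-up and female rates per 100,000 per year from Table 1.

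| Disease, window | Rate | Expected cases | P(more than 10) in one cohort |
|---|---|---|---|
| GBS, 2 months | 0.4 to 2 | 0.04 to 0.22 | below 1e-6 |
| ITP, 6 months, UK rates | 2.7 to 4.9 | 0.88 to 1.59 | below 1e-6 |
| ITP, 6 months, US rates | 1.5 to 15 | 0.49 to 4.88 | at most 0.012 |

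Table 1 gives no rate for autoimmune haemolytic anaemia. If the 10-case threshold in 9.7.6 means the two female cohorts together, the expected ITP count is at most 2 × 1.59 = 3.19 at UK rates, with P(more than 10) about 0.0005. At the highest US rate it is 2 × 4.875 = 9.75, with P about 0.39.

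A 26% distortion of 0.22 GBS cases is about 0.06 of a case. A 17% distortion of 1.59 ITP cases is about 0.3 of a case.

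**The case against.** The strongest reply is that the sections can be reconciled: 9.1.2 names the source of the dates and 9.2.2 only their limits. The protocol never calls the dates themselves uniform. That word describes the generator, where the selection of exposed subjects is explained, and RANUNI can equally pick from a list. The parenthesis after the historical limits can be read as the 9.1.2 rule. Annex 5, which holds the stepwise identification of the cohorts, is not reproduced. This stands in part: uniform assignment is the plain reading of 9.2.2, not a stated fact. But the parenthesis follows two limits that are exactly the exposed limits less 3 years, so it reads naturally as the shifted span, and the sentence on concurrent males has no such link.

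A second reply is that 9.1.2 also plans matching on one-year age class at the reference date, which would bound any age shift, and that age group is in the model. That holds if this matching is carried out. However, 9.2.2 selects by birth cohort and region, and the model's two age bands are wide.

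A third reply is that the effect may be negligible. Section 9.2.1 names no season, the catch-up was phased, and no seasonality is given for the three diseases. This stands, and it is why the range in the working includes 3-4%.

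A reader might go further and infer that season is confounded with exposure in the study's risk ratios. The documents do not support that. The co-primary composites use 12 months, the self-controlled analysis uses no unexposed dates, and the short-window analyses are non-confirmatory. A modelled ratio is unlikely for GBS, and for ITP at UK rates, however the threshold is read.

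**Conclusion.** The conflict over time zero is real and should be resolved before the cohorts are drawn. If first doses were uneven over the calendar, the 9.2.2 rule gives the unexposed cohorts a different start-date distribution from the exposed cohort. The possible consequences are a seasonal mismatch in the 2- and 6-month windows and an age mismatch within birth cohorts.

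The size cannot be fixed from the protocol. It runs from 3-4% to about 26% at 2 months and 17% at 6 months, and rests on assumed dose timing, assumed ±30% sinusoidal seasonality and the least favourable peak month. The primary analysis has no seasonal bias. What is exposed is a set of descriptive rates, reported per cohort without a case threshold, that will be read side by side although they rest on very few cases: about 0.04 to 0.2 for GBS and up to about 5 for ITP per cohort. The case for changing the text is the contradiction and the low cost of removing it, not a demonstrated bias.

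**What to change.** Replace the span rule in 9.2.2 with the 9.1.2 rule:

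1. For each unexposed subject, draw the reference date at random from the first-dose dates of exposed girls in the corresponding birth cohort-region cell, with the birth cohort shifted by 3 years for the historical cohorts.
2. Use the drawn date itself for concurrent males, and that date less 3 years for both historical cohorts.
3. Then apply eligibility and check one-year age class at that date.

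Drawing within cells is an addition to the wording of 9.1.2. Birth cohort and region are known before a date is assigned, which avoids the circularity of using age at the reference date to define the cell. The cost is a change to the sampling program and a few sentences of protocol text, with no further subjects or data. Tabulating exposed first doses by month would also show how far the two rules differ in practice.

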9.2.3. Number of subjects

For the cohort design, the target sample size is 65,000 subjects for each cohort. Refer to Section 9.5 for a detailed description of the estimation of the sample size.

9.2.4. Inclusion criteria

Note: Other vaccines are allowed in this study regardless of the time of administration and the time interval between subsequent doses.

9.2.4.1. Inclusion criteria for the exposed female cohort

Exposed females must satisfy ALL the following criteria at study entry:

- Female aged from 9 to 25 years at the reference date (01 September 2008 through 31 August 2010)
- Recorded in the CPRD GOLD for at least 12 months before the reference date
- The first dose of Cervarix received between 01 September 2008 through 31 August 2010, Full date (day/month/year) of Cervarix vaccination(s) available
- Subject defined as acceptable in CPRD GOLD

9.2.4.2. Inclusion criteria for the unexposed historical female cohort

Unexposed females must satisfy ALL the following criteria at study entry:

- Female aged 9 to 25 years at the reference date (01 September 2005 through 31 August 2007)
- Recorded in the CPRD GOLD for at least 12 months before the reference date
- Subject defined as acceptable in CPRD GOLD

9.2.4.3. Inclusion criteria for the unexposed concurrent male cohort

Unexposed concurrent males must satisfy ALL the following criteria at study entry:

- Male aged 9 to 25 years at the reference date (01 September 2008 through 31 August 2010)
- Recorded in the CPRD GOLD for at least 12 months before the reference date
- Subject defined as acceptable in CPRD GOLD

9.2.4.4. Inclusion criteria for the unexposed historical male cohort

Unexposed historical males must satisfy ALL the following criteria at study entry:

- Male aged 9 to 25 years at the reference date (01 September 2005 through 31 August 2007)
- Recorded in the CPRD GOLD for at least 12 months before the reference date
- Subject defined as acceptable in CPRD GOLD

9.2.5. Exclusion criteria

9.2.5.1. Exclusion criteria for all cohorts

- Subjects with a diagnostic code of any auto-immune disease during the year prior to the reference date.
- Subjects who received at least one dose of unspecified HPV vaccine or Gardasil at any time before the reference date.
- Subjects who have been included in the other cohort.

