95% confidence interval: 1.08-1.56) but the authors reported that "there was no consistent elevation in incidence for autoimmune thyroid conditions in the vaccinated cohort [IRR = 0.72 (0.50-1.01) for Graves' disease] and several confirmed new-onset autoimmune thyroid condition cases were likely pre-existing cases at the time of vaccination" [Chao, 2011].

GSK also committed to develop a post-licensure study of NOAD as outlined in the 2009 approval letter for Cervarix in the US:

"To conduct an observational study in a US managed care organization to evaluate the incidence of new onset autoimmune disease among at least 50,000 Cervarix recipients. The final protocol will be submitted by March 2010. Projected completion of patient accrual, subject to vaccine uptake, will be completed by March 2013. Projected study completion, subject to vaccine uptake, will be completed by September 2014. The final study report is projected to be submitted by March 2015 (6 months after study completion)".

In order to address this regulatory commitment, GSK initiated an observational cohort study to assess the risk of NOAD within 12 months following the administration of at least one dose of Cervarix (exposed) versus a non-Cervarix vaccinated cohort (unexposed). This study (e-track: 113522, EPI-HPV-015) planned to include 140,000 females, aged 9 to 25 years, enrolled in US health plans. Based on the low incidence of NOAD in this age-group, composite endpoints were defined and agreed with the FDA. Its primary objective is to evaluate whether there is an increased incidence of neuroinflammatory NOAD or other NOAD within 12 months following the administration of at least one dose of Cervarix. Data are retrieved from a large insurance administrative claims database (HealthCore Integrated Research Database (HIRD), HealthCore Inc., WellPoint, New York, US) which includes data from 14 health plans distributed throughout the US, representing claims information from the largest commercially insured population in the US.

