9.3. Variables

9.3.1. Primary endpoint

• Occurrence of new onset of confirmed⁴ autoimmune disease during the period of one year following administration of the first dose of Cervarix (risk period) among an exposed cohort and during an equivalent time period in the unexposed cohorts for the following two co-primary composite endpoints:

[1] Neuroinflammatory/ophthalmic autoimmune diseases:

- Multiple Sclerosis
- Transverse myelitis
- Optic neuritis
- Guillain-Barré syndrome, including Miller Fisher syndrome and other variants
- Other demyelinating diseases:
 - Acute disseminated encephalomyelitis, including site specific variants: e.g. non-infectious encephalitis, encephalomyelitis, myelitis, myeloradiculomyelitis
 - AI peripheral neuropathies and plexopathies (including chronic inflammatory demyelinating polyneuropathy, multifocal motor neuropathy and polyneuropathies associated with monoclonalgammopathy).
- Auto-immune uveitis

[2] Other autoimmune diseases:

- Systemic lupus erythematous
 - Autoimmune (AI) disease with rheumatologic conditions:
 Rheumatoid arthritis (RA)

⁴ Auto-immune disease diagnosis ascertainment by an expert physician panel (Section 9.4.2).

- Juvenile rheumatoid arthritis (JRA)
- Still's disease
- Psoriatic arthritis
- Ankylosing Spondylitis
- AI haematological conditions:
 - Idiopathic thrombocytopenic purpura (ITP)
 - AI haemolytic anaemia
- AI endocrine conditions:
 - Type 1 diabetes mellitus
 - AI thyroiditis including Hashimoto's disease, Graves' /Basedows' disease
- Inflammatory bowel / hepatic diseases:
 - Crohn's diseases
 - Ulcerative colitis
 - Autoimmune hepatitis

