9.4.2. Data source for case ascertainment

First, the CPRD GOLD is based on data from GPs, while most auto-immune diseases would probably be diagnosed in specialist settings. Consequently, the number of auto-immune diseases, the quality of the information, and the diagnostic certainty might be lower compared to other databases that include hospital data only. In particular the specific information related to the onset of clinical symptoms, and radiological and biological data associated with the etiologic diagnosis of auto-immune diseases may not all be available in the CPRD GOLD database and associated resources. Besides, not all general practices participating to CPRD GOLD have consented to the linkage between CPRD GOLD primary care data and HES data (current linkage around 50% as of Q3 2012). Specific algorithms for each outcome of interest have been developed (Annex 5)

116239 (EPI-HPV-040 VS UK) Protocol FDA - EMA PASS Final Version 1

and available "free text" that is related to auto-immune disease diagnosis will be requested from CPRD GOLD, when needed.

Moreover, in a recent study by [Chao & Jacobsen, 2012], the authors recommended that expert case review of medical records is used in autoimmune safety studies, and case identification can be expanded by use of laboratory test results and other relevant measures in addition to specific ICD-10 diagnosis codes.

[figure not shown]
The ascertainment of the etiologic diagnosis and date of disease onset for all identified auto-immune diseases will be performed by a contract research organisation (CRO) to ensure the correct classification of each case. The CRO will review all subject data retrieved from CPRD GOLD including medcodes (including clinical, laboratory, and treatment files), the relevant "free text" and HES (including specific ICD-10 diagnostic codes), when available. They will assess whether the aetiology of the auto-immune disease is confirmed or not and whether the date of disease onset falls within the observation period of the study, which is one year after the reference date.

[figure not shown]
In the event that the aetiology or the date of onset could not be confirmed, a second review step will be conducted with an expert physician panel to reach an agreement about the case ascertainment, and, if they cannot reach an agreement, then the different clinical opinion of the experts will be listed. The experts will be blinded with regards to HPV vaccine exposure.

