9.7.3. Subject disposition

Subject disposition will be summarized by cohort and overall by computing:

- Number of screened subjects.
- Number (%) of non-eligible subjects for each of the following reasons of non-eligibility:
 - Diagnostic code of NOAD during the year prior to the reference date (for all cohorts);
 - Subject not actively registered with the practice during the study period (for all cohorts);
 - Subject not flagged as acceptable in CPRD GOLD (for all cohorts);
 - Subject not recorded for at least 12 months within CPRD GOLD at reference date;
 - At least one dose of unspecified HPV vaccine or Gardasil at any time before the reference date(for all cohorts);
 - At least one dose of Cervarix vaccine at any time before the reference date (for unexposed cohorts);
 - The first dose of Cervarix received before 01 September 2008 or after 31 August 2010 (for the exposed female cohort).
- Number of eligible subjects in each cohort.
- After frequency matching for age and for practice-region, number of included subjects in each cohort.

A detailed, comprehensive list of reasons for elimination from exposed and unexposed cohort analyses will be established at the time of data cleaning.

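### The one-year look-back leaves older coded autoimmune disease in all four cohorts, so the new-onset endpoint depends on a case review that has no stated rule for earlier codes

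*Protocol*

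**What the plan says.** Protocol Section 9.2.5.1 removes "Subjects with a diagnostic code of any auto-immune disease during the year prior to the reference date", and Section 9.7.3 uses the same one-year window as a reason for non-eligibility. The next exclusion in Section 9.2.5.1 has no such limit: "Subjects who received at least one dose of unspecified HPV vaccine or Gardasil at any time before the reference date". Section 9.2.5.2 does the same for prior Cervarix in the unexposed cohorts.

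The inclusion criteria ask for a minimum history: "Recorded in the CPRD GOLD for at least 12 months before the reference date". Longer records exist, since Section 9.4.1 gives a median follow-up of 5.0 years.

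The primary endpoint in Section 9.3.1 is "Occurrence of new onset of confirmed" autoimmune disease within one year. Section 9.1.2 notes: "Some NOAD present with a chronic disease pattern of relapse over time e.g. multiple sclerosis or systemic lupus erythematous".

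The safeguard is case review:
- Section 9.3.3.2: free text is read for the date of first symptoms.
- Section 9.4.2: a contract research organisation reviews all retrieved data for every identified case and judges whether onset falls in the year after the reference date. Unclear cases go to an expert panel blinded to HPV vaccine exposure.

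The same section warns that "the specific information related to the onset of clinical symptoms" may not all be available and that hospital linkage is around 50%.

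**The concern.** For an endpoint of new onset, the subjects at risk of a given disease are those who have not yet had it. Under a one-year window, a subject with a code for uveitis, thrombocytopenic purpura or thyroid disease three years earlier, and none in the last year, enters the cohort and adds person-time. The next code makes that subject a potential case. The entry criteria do nothing to prevent this, so the task passes entirely to the judgement of onset date.

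Pre-existing disease that is accepted as new adds cases unrelated to vaccination. If it does so equally in exposed and historical cohorts, the rate ratio moves towards 1. In a safety study that is the direction that hides harm.

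The protocol's own background shows that review can be imperfect. Of the cited quadrivalent HPV vaccine study, which included case review, Section 7 reports that "several confirmed new-onset autoimmune thyroid condition cases were likely pre-existing cases at the time of vaccination". Thyroiditis belongs to the second co-primary endpoint here.

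**Working it through.** **1. Who remains eligible.** Section 9.2.5.1 is the only criterion on prior autoimmune disease. No other criterion in Sections 9.2.4 to 9.2.5 removes a subject whose only code is more than a year old. This holds for exposed females, historical females and both male cohorts.

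**2. Whether review closes the gap.**
- Section 9.4.2 does not say how far back the reviewers' data go, or that an earlier code of the same disease rules out new onset.
- If the experts disagree, their opinions are listed. No default classification is given.
- Section 9.9 names time to onset of first symptoms as a limitation.
- The onset check covers one year after the reference date. The self-controlled analysis (Section 9.7.9.2) has its risk period in months 0 to 12, a buffer in months 12 to 18 and its control period in months 18 to 30. The document does not say that the check extends to the control period.
- Section 9.7.5.1 adds a sensitivity analysis, used if more than 5% of events have an unknown or incomplete date, that counts those events inside the risk period in all four cohorts. An undated relapse would then count as new.

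**3. Effect on the rate ratio.** Let *a* be the rate of old disease accepted as new, as a fraction of the true baseline rate, equal in both cohorts:

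observed RR = (RR + a) / (1 + a)

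The documents give no value for *a*. I assume 0.10, 0.25 and 0.50.

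The plan states no figure on this point. Its nearest figures are the detectable ratios in Section 9.5.1 (50,000 per cohort, 80% power, two-sided alpha 0.05): 18.7, 3.7, 2.0 and 1.6 at 1, 10, 50 and 100 per 100,000 person-years. A pooled-variance comparison of two proportions gives 18.49, 3.72, 1.96 and 1.64, so these reproduce closely and are not in dispute. I use the same formula for power, with n = 50,000:

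power = Φ{ [ |p1 − p0|·√n − 1.96·√(2·p̄·(1 − p̄)) ] / √[ p0(1 − p0) + p1(1 − p1) ] }

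where p0 = baseline × (1 + a) and p1 = baseline × (RR + a).

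| a (assumed) | True RR 2.0 seen as | Power at 50/100,000 | True RR 3.7 seen as | Power at 10/100,000 |
|---|---|---|---|---|
| 0 | 2.00 | 82.3% | 3.70 | 79.5% |
| 0.10 | 2.10/1.10 = 1.91 | 79.8% | 3.80/1.10 = 3.45 | 77.9% |
| 0.25 | 2.25/1.25 = 1.80 | 76.2% | 3.95/1.25 = 3.16 | 75.4% |
| 0.50 | 2.50/1.50 = 1.67 | 70.6% | 4.20/1.50 = 2.80 | 71.5% |

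If review rejects every old case, a = 0 and the case counts are unbiased.

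**4. Unequal leakage.** Under a true ratio of 1, leakage of 25% in one cohort and 10% in the other gives 1.25/1.10 = 1.14, or 1.10/1.25 = 0.88 the other way round. Nothing in the documents shows that leakage is unequal. The calculation only shows why the look-back length should be the same in every cohort.

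**The case against.** Entry to the cohort does not make a subject a case. Every identified case has its onset date reviewed against codes, laboratory and treatment files, free text and, where linked, hospital data. Doubtful cases go to a panel blinded to HPV vaccine exposure. A subject with a visible earlier code is the easiest to reject, and neither free text nor hospital linkage is needed for that. Missing onset data matter most where there is no earlier code, and no rule based on codes can help there. The one-year window also has a rationale: it equals the minimum record required, so every subject has it in full. Annex 5, which holds the case algorithms, is not reproduced and may already require a first-ever code. Section 9.9 itself discloses that imperfect specificity biases towards the null.

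Most of this stands. It limits the point to cases that slip through review, and means that no size can be claimed from the documents. It does not supply the missing rule: the text never says that an earlier code disqualifies a case, or that reviewers see the full earlier record.

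Two stronger readings are tempting and are not supported:
- A reader might infer that subjects with older disease will simply be counted as new onset. The review in Sections 9.3.3.2 and 9.4.2 stands between the code and the endpoint.
- A reader might infer that GP contact at vaccination prompts recording of old disease and so adds false cases among the exposed. Section 9.2.1 says the programme was delivered largely through secondary schools, so the first dose was usually not a GP visit.

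The cited precedent also has limits. The protocol calls those cases only likely pre-existing, and gives neither that study's look-back nor whether earlier codes existed. They may have been undiagnosed disease, which a look-back on codes would miss.

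**Conclusion.** The point holds as a minor design weakness. The one-year window leaves older coded disease in all four cohorts, and the exclusion of pre-existing disease from the endpoint then depends on a review without an explicit rule for earlier codes and with an onset check worded only for the first year. Review should reject most such cases.

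If some leak through equally, the rate ratio is diluted: a true 2.0 is seen as 1.91 to 1.67 under assumed leakage of 10% to 50% of baseline, and as 2.0 under none. These percentages illustrate the direction and scale; they are not estimates. In the self-controlled analysis the direction depends on which period lets more old disease through, and the document does not settle that. The sample-size figures are unaffected.

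**What to change.** For each endpoint disease, count a case as new onset only if the available record holds no code for that disease at any time before the reference date. Fix one maximum look-back length for all four cohorts, so that the three-year calendar offset does not give the later cohorts a longer history. Apply the same rule to the risk and control periods of the self-controlled analysis, and state that the onset check covers both. Give reviewers the full prior record over that look-back. Keep the current 12-month rule as a sensitivity analysis.

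The rule should be disease-specific. Excluding anyone with any autoimmune code ever would also remove subjects who remain at risk of a different, genuinely new disease.

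The cost is one derivation step on data already held, and some cases would no longer need a judgement on onset. Recorded history varies between subjects, so some older disease will still be missed, and a few cases will be removed from the analysis.
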